Parallel group unicentric randomized clinical trial. Prospective primary care intervention study.

For randomization, randomly generated numbers will be used in closed envelopes controlled by a professional outside the study. Subsequent masking is not appropriate for the patient. The randomization unit will be the patient.

Sample

Open-label (or non-blind) unicentric randomized clinical trial of parallel groups. Simple random sample of patients who go to an appointment with their family doctor.

Inclusion criteria: Patients older than 18 years old who go to their family doctor by appointment.

Exclusion criteria:

- Patients with language barrier
- Patients younger than 18 years (AD not provided for by law) (28)
- Patients with altered decision-making ability according to computerized clinical history by coding in health problems or mentioned in a clinical course of computerized medical history (eCAP): cognitive impairment, dementia, mental retardation diagnosed. Although there are studies on attitudes towards ADs of people with early cognitive impairment (Minimental > 18), it was decided to discard because the intervention should be brief. The cited study also concludes that this type of patients prefer to delegate decisions to the family. (29)
- Patients who come spontaneously to their family doctor.
- Patients who have already been recruited previously in the study. Patients who may visit by appointment only on more than one occasion will only participate once and subsequent visits for recruitment will be excluded. In addition, there will be no reinforcement of the study intervention in these visits.
- Patients who have already formalized the ADs.
- Patients who do not wish to participate in the study.

Calculation of sample size: In order to know the magnitude of the effect of similar studies in primary care with similar interventions (written and oral information vs no intervention), the Wissow study (25) was chosen, where the proportion of VAD obtained in intervention group was 7.8% vs. <1% in the placebo group.

In calculating proportions in cohort studies or clinical trials:

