Accepting an alpha risk of 0.05 and a beta risk of 0.2 in a bilateral contrast, 165 individuals in the intervention group and 165 in the control group are required to detect a minimum relative risk of 7.8 (= 7.8% / 1%) taking the rate of VAD in the intervention group as 7.8% and in the control group of 1%. A rate of loss has been estimated for refusing the 10% share. The POISSON approximation has been used in the statistical calculator GRANMO, version 7.12 online (Program of Research in Inflammatory and Cardiovascular Disorders, Institut Municipal de Investigació Mèdica, Barcelona, Spain)

Although hypothetically no losses are expected, they may have been relinquished to participate for different reasons. In order to avoid a selection bias produced by the relationship of giving up with the fact of wanting to do a VAD, patients refusing to participate will be excluded and the motive, age and sex will be collected to compare if there are differences between the two groups regarding these characteristics.

Ambit

Florida Nord de l'Hospitalet de Llobregat Primary Care Center, an urban area with a population of approximately 25,000 people. Multicultural neighborhood with low socioeconomic status. The follow-up time for the intervention will be 3 months.

Information sources

Records of shared clinical history in eCAP. Patient questions about independent variables if they are not recorded.

Recruitment procedure

Consecutive recruitment: They will be consecutively obtained from different quotas (both afternoon shift and morning shift) so that the sample is representative of the study population.

Participate the quotas of the center whose doctor in charge has wanted to participate in the study. In order to avoid a selection bias and a more active doctor than another to have more patients represented in the study, a mechanism will be established whereby everyone will have the same probability of recruiting a similar number: the first 6 visits of each day for 8 days. The recruitment period will be made from 01/06/2015 to 09/30/2015, until the sample is completed. The follow-up period will be 3 months for each patient (both intervention and control).

A list of random numbers will be created and divided among the 7 consultations of the participating physicians in the study. Each day, the first 6 visits to the list will be recruited for 8 days prior appointment or until the sample is completed.

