Patients who fall into a control group will only be attended to their reason for visiting and will be asked for the necessary data to obtain the independent variables if they do not appear in their history. If the patient in this group wants the information, he will be excluded from the study because he "refuses to participate."

If the patient, both the control group and the intervention group, has some exclusion criteria, it will be recorded as a screening failure and their randomization number will not be re-used for the next patient.

All patient information will be kept confidential.

Result or dependent variables

They will be obtained at the moment that the patient shows interest in the intervention, or else, by asking by appointment or by telephone within 3 months of their recruitment:

- Interest in information about DVA: yes, no. Number of patients who have come to their family doctor (MF) to request information or have been interested by telephone in each group.

- Implementation of DVA: yes, no. Number of patients in each group.

In case of not being able to contact the telephone patient or face to face at 3 months, the DVA registration will be viewed at the Primary Care Clinic Station (eCAP), which is the computerized medical history program used by all professionals in the network of primary care of the Institut Català de la Salut (ICS).

The document can be accessed from:

- HC3 - Notices: shared clinical history projects in Catalonia.

- Dades del pacient: Documents of anticipated voluntats

Registration from the Department of Health is autonomous, although not done in the ABS. From other institutions, the patient is always advised to take the DVA to his health center.

- Open question to know the reason that has led to formalize the DVA, both to patients in the intervention group and control.

- Time to perform the DVA from the day of recruitment, expressed in days, to both the intervention and control patients.

Limitations and ethical considerations

- Possible increase in response in the intervention group due to the link with the family physician (participation bias). It could be wrongly concluded that the intervention is effective when compared to the control group. Randomization of the sample is intended to partially avoid this problem.

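### The advance directive register is consulted only when a patient cannot be reached at 3 months, so a completion after an early assessment may be missed

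*Protocol*

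**What the plan says.** The protocol section on result or dependent variables gives three routes to the outcomes, which include interest in an AD and completion of one.

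- The first is triggered by the patient: "They will be obtained at the moment that the patient shows interest in the intervention".
- The second is an alternative to the first: "or else, by asking by appointment or by telephone within 3 months of their recruitment".
- The third is a fallback to the register: "In case of not being able to contact the telephone patient or face to face at 3 months, the DVA registration will be viewed".

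The same section asks for a further variable: "Time to perform the DVA from the day of recruitment, expressed in days, to both the intervention and control patients". It does not say where the completion date comes from.

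Elsewhere, the recruitment procedure sets the window: "The follow-up period will be 3 months for each patient (both intervention and control". The information sources section lists eCAP in general terms: "Records of shared clinical history in eCAP. Patient questions about independent variables if they are not recorded". The design is "Open-label (or non-blind) unicentric randomized clinical trial of parallel groups", and the schedule of activities has the participating physicians conduct the follow-up. The SAP repeats the objectives and tests but says nothing about how or when AD status is established.

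**The concern.** The objective concerns what happens over 3 months, so each patient's AD status should be known at 3 months. The outcome section does not secure this. A status taken when interest is first shown is taken early, and under the intervention section interest normally precedes completion: the patient leaves contact details or books an appointment and is then helped with the document. The patients most likely to complete an AD are therefore those whom the text allows to be assessed before they have done so.

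The source also varies. Reached patients are classified by their own answer, and unreached patients by the register. Neither source is checked against the other, and no table is planned that would show how often they disagree.

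At stake is mainly the count of completed ADs. It is expected to be small and it is the basis of the sample size. Time to AD is also exposed, because an AD that is not seen has no date.

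**Working it through.** **1. The passages side by side**

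| Question | What the protocol gives |
|---|---|
| Length of follow-up | 3 months for each patient, both arms (recruitment procedure) |
| When status is recorded | when interest is shown, or else on asking *within* 3 months (outcome section) |
| When the register is used for an outcome | when contact fails *at* 3 months (outcome section) |
| Update of a status recorded early | not stated |
| Register check for reached patients | not stated |
| Source of the completion date | not stated |

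**2. Which outcomes can be affected**

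- *Patient recorded as interested early, AD made later and not seen.* The combined outcome is already positive and does not change. Completion is wrongly negative, and time to AD is lost.
- *Patient asked early, answers no, not asked again, AD or interest later.* The combined outcome is wrong, and so are completion and time to AD if an AD was made. This case arises only if *within 3 months* is read literally and there is no second contact.

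**3. The plan's own sample size**

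Inputs from the sample size section: 7.8% vs 1%, two-sided alpha 0.05, power 80%, 10% loss, Poisson approximation.

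n = (1.960 + 0.842)² × (p1 + p2) / (p1 − p2)² = 7.849 × 0.088 / 0.068² = 149.4 per arm.

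Allowing for 10% loss: 149.4 / 0.90 = 166.0 (or 149.4 × 1.10 = 164.3). Both lie within two patients of the stated 165, so the figure reproduces. It is a calculation for AD completion alone.

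**4. Illustration: power for completion if some ADs are missed**

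Let m be the share of completions missed, assumed equal in both arms. The documents give no value for m. The observed rates become 0.078(1 − m) and 0.01(1 − m). Power is the exact binomial probability of a two-sided 5% result favouring the intervention. The smaller sample is 165 × 0.90 = 148.5, taken as 148.

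| m (assumed) | Expected completions, 148 per arm | Power, 148 per arm (Fisher / chi-square) | Power, 165 per arm (Fisher / chi-square) |
|---|---|---|---|
| 0 | 11.5 vs 1.5 | 79% / 87% | 84% / 91% |
| 10% | 10.4 vs 1.3 | 73% / 82% | 79% / 87% |
| 20% | 9.2 vs 1.2 | 65% / 77% | 72% / 82% |
| 30% | 8.1 vs 1.0 | 56% / 70% | 64% / 75% |

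With about 11.5 completions expected in the intervention arm, missing 20% means losing 11.5 − 9.2 = 2.3 of them.

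**The case against.** The strongest reply is that a contact at 3 months was intended and that only an operational detail is unwritten. Several things support this:

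- The fallback applies when contact fails at 3 months, which presupposes an attempt then.
- Follow-up is 3 months for each patient in both arms.
- The schedule places inclusion in September and last follow-up in December. Its years conflict, but the months fit.
- Days to AD, and the reason for making one, cannot be collected if status is frozen at first interest.
- The team offers help with the document, so it would often know of a completion.
- *Within 3 months* may simply be a translation of *at 3 months*.

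This stands as a statement of probable intent. It does not supply a rule that every patient is contacted at 3 months, or that a patient recorded early is assessed again. Recording at the moment of interest is explicit and does not depend on how *within* is read.

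A second reply is that the combined outcome is protected once interest is recorded. That is right, and it limits the point. Completion nevertheless remains a separate outcome, the subject of the first hypothesis and the basis of the sample size.

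A third reply is that the missed shares are invented. They are assumptions. With all 165 per arm analysed and 10% missed, power is still 79%/87%, about the planned 80%.

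A reader might also infer that open-label follow-up by the participating physicians biases the comparison between arms. Early assessment could well be more frequent in the intervention arm, since only that arm is invited to respond. The documents do not show that it is, or which way the result would move.

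**Conclusion.** The point holds as a gap in how AD completion is ascertained. As written, completion may be recorded before the 3-month window closes with no stated update, and the source depends on whether the patient can be reached. For patients already recorded as interested, the effect is confined to completion and time to AD. The combined outcome is at risk only for a patient who is asked early, says no and is not asked again.

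Two stronger readings are not supported. One is that the main comparison is biased: neither a difference between arms nor its direction can be derived from the text. The other is that the trial as a whole is underpowered for this reason: the power figures concern completion only and rest on assumed shares missed equally in both arms. Under those assumptions, with 148 per arm, the loss is 6 points (Fisher) or 5 points (chi-square) at 10% missed, and 14 or 10 points at 20%, using the rounded figures.

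This is a worthwhile, cheap improvement, not a fundamental fault. The conclusion rests on the supplied text. Part of the protocol was not available, and the annexes are in a separate document.

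**What to change.** Add to the outcome section and the SAP:

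1. Check the AD record in eCAP/HC3 for all randomised patients in both arms at the same point, 3 months after recruitment, in addition to asking the patient.
2. Count an AD as completed if either source shows it within 3 months of recruitment.
3. For time to AD, use the registered date where there is one, otherwise the date the patient reports.
4. Report, by arm, the completions found only in the register and those found only by patient report.

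The cost is about 330 lookups (165 + 165) in a system the protocol already uses, and the ethics section already provides for signed consent to eCAP access. The objective, sample size and tests stay as they are.

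One limit remains. ADs made elsewhere and not registered are still seen only through patient report, because patients are merely advised to bring them to the health centre. The counts in item 4 make this visible but do not remove it.

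If the protocol already intends a 3-month assessment of every patient, saying so would close the timing gap. The dependence of the source on reachability would remain until the register is checked for all.

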EFFECTIVENESS OF A BRIEF INFORMATION ABOUT ADVANCE DIRECTIVES IN PRIMARY CARE: A RANDOMIZED CLINICAL TRIAL

Promoter of the study: Proposal of own initiative of the researcher [name] to present as thesis of the Master's Degree Design and Analysis of Clinical Investigations of the Official College of Physicians of Barcelona (COMB) of the thesis student [name].

Family Physicians' Team of the Basic Health Area Florida Nord de l'Hospitalet de Llobregat:

-	- [name]	- [name]
-	- [name]	- [name]
-	- [name]	- [name]
-	- [name]	

Study to be presented in the design phase to the Master of the COMB.

ABSTRACT

The knowledge and completion of advance directives (ADs) by the population is generally low. Primary care could develop a very important role to inform and assist in the preparation of this document because of its accessibility.

Objective: To evaluate the effectiveness of an oral brief information and a brochure administered in primary care to improve the proportion of ADs records.

Design: Randomized clinical trial.

Ambit: 7 offices from a urban health center in Hospitalet de Llobregat which serves about 25,000 users older than 18 years.

Material and methods

It will be administered randomly triptych and oral brief information about the existence of advance directives for people over 18 to attend the appointment of their family doctor for any reason (intervention group). It will be given the possibility of more extensive information if they wish and collaboration will be offered for the advance directive according to patient preferences. The control group will not receive any information. Follow-up: 3 months. Variables will be: number of people interested in ADs, number of ADs made and demographic data (gender, age, education level, race, comorbidities, religion, testament) in both groups. Statistical analysis: multiple linear regression, Poisson and Cox as response analyzed, with the intervention/control group as the main variable adjusting for potential confounders. Bivariate comparison using Student t test or Mann-Whitney test (continuous variables) and chi-square or Fisher's exact test (categorical variables). 165 subjects were required in the control group and 165 in the intervention group.

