Regarding intervention studies to increase the records of DVA performed in Primary Care, we have that of Donahue et al. who obtained a 32.5% increase in VAD by mailing the information prior to the arranged visit with their family doctor and completing it in successive visits in a period of 3 months (24).

Wisow et al., In a quasi-experimental study of 1 year duration, promoted the anticipated will in over 65 in health centers through oral and written education (a letter prior to a control visit and a subsequent reminder visit) administered by

family doctors and used another health center as a control. The result was an increase of 7'8% of registrations with respect to <1% in the control center (25). According to another study in Primary Care (Ramsaroop, 2007), the information leaflet alone is not effective and the best would be multiple educational visits to promote the attitude change phase towards the ADs procedure (26).

Hypothesis of the study

Giving brief oral and written information to patients visited by your family doctor on a prior appointment increases the proportion of DVA records by 8%.

Providing a brief oral and written information to patients visited by their family doctor in a previous appointment increases the proportion of people interested in this right (there is no previous bibliography on this data).

People who write a DVT are usually older, white, women, have more children, have a will and have more comorbidity than those who do not.

MAIN OBJECTIVE

To evaluate the effect of brief oral and written information on the advance directive document (DVA) administered by primary care physicians, compared to usual clinical practice, on the proportion of persons interested in or performing the VAD in 3 months in the adult population (over 18 years old) who attend a Primary Care appointment.

SECONDARY OBJECTIVES

Evaluate the baseline characteristics of those who perform or are interested in VAD (whether they are in the control or intervention group).

To assess the baseline characteristics of those performing the DVA and those not within the intervention group.

Evaluate the reasons why patients finally formalize the document by open question (will be categorized if there is a limited number of responses, otherwise the reasons will be described qualitatively).

Evaluate the average time to perform the DVA from the day of the patient's recruitment.

MATERIAL AND METHODS

Design

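### AD completion is framed as a record, but patients who are reached can be scored on an unconfirmed answer and unreached patients on the register

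*Protocol*

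**What the plan says.** Three places in the protocol express the AD outcome as a record.

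- The abstract's objective is "to improve the proportion of ADs records".
- The first hypothesis is that the information "increases the proportion of DVA records by 8" per cent.
- The study used for sizing is reported, under Studies carried out in Primary Care, in terms of registrations: "The result was an increase of 7'8% of registrations with respect to <1% in the control center". Its rates set the sample size, "taking the rate of VAD in the intervention group as 7.8% and in the control group of 1" per cent.

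The Information sources section names eCAP records, and mentions questions to the patient only for independent variables.

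The section Result or dependent variables works differently. Outcomes are obtained when the patient shows interest or by asking at an appointment or by telephone. The register is the fallback: "In case of not being able to contact the telephone patient or face to face at 3 months, the DVA registration will be viewed". On ADs made outside the centre it adds: "From other institutions, the patient is always advised to take the DVA to his health center".

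Neither the protocol nor the SAP requires a yes to be checked, says which source prevails if the two disagree, or plans a sensitivity analysis on recorded ADs.

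**The concern.** The same event has two sources, and which one applies depends on whether the patient was reached. Someone who filled in the form without formalising it, who confuses it with the will on material goods that the trial also asks about, or who answers to please the doctor would count as an event if reached and as a non-event if not.

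The trial is open label, and intervention patients are told that a reply is awaited within 3 months. The protocol's own limitations section warns that the link with the family physician may raise response in the intervention arm and lead to a wrong conclusion of effectiveness. Its stated remedy is randomisation, which does not act on reporting after allocation.

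False answers that are equally common in both arms dilute the effect and cost power. False answers concentrated in the informed arm can create an effect. Either way, the estimate is no longer the proportion of records that the hypothesis names.

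**Working it through.** **Inputs (protocol, Calculation of sample size).** Two-sided alpha 0.05 and power 80% ("Accepting an alpha risk of 0.05 and a beta risk of 0.2 in a bilateral contrast"); rates 7.8% and 1%; 10% loss; Poisson approximation; "165 individuals in the intervention group and 165 in the control group are required to detect a minimum relative risk of 7.8".

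**Reproducing the plan's figure.** n = (1.960 + 0.842)² × (p1 + p2) / (p1 − p2)² = 7.849 × 0.088 / 0.068² = 149.4 per arm. Allowing for 10% loss, 149.4 / 0.9 = 166.0 or 149.4 × 1.1 = 164.3. Both agree with the stated 165. The evaluable number used below is 165 × 0.9 ≈ 149 per arm.

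**Expected true events.** At 165 per arm: 165 × 0.01 = 1.65 control and 165 × 0.078 = 12.9 intervention. At 149 per arm: 1.5 and 11.6.

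**Model.** Let f be the share of patients without an AD who are scored yes. The observed rate is p + (1 − p)f. I assume that all patients are reached and that no true AD is missed. The documents give no value for f, so 0 to 3% is an assumed range.

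**Equal f in both arms.** Exact binomial enumeration, two-sided 5% tests, 149 per arm:

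| f | Control | Intervention | Risk ratio | Power, chi-square | Power, Fisher |
|---|---|---|---|---|---|
| 0 | 1.00% | 7.80% | 7.8 | 87% | 79% |
| 1% | 1.99% | 8.72% | 4.4 | 77% | 67% |
| 2% | 2.98% | 9.64% | 3.2 | 67% | 58% |
| 3% | 3.97% | 10.57% | 2.7 | 60% | 52% |

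At f = 1%, 0.99 / 1.99, or half, of the control events are false.

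**False answers in the intervention arm only, true rate 1% in both arms.** Probability of a significant result favouring the intervention, 149 per arm (nominal 2.5%):

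| f | Observed rates | Fisher | Chi-square |
|---|---|---|---|
| 1% | 1.99% vs 1% | 2% | 9% |
| 2% | 2.98% vs 1% | 9% | 21% |
| 3% | 3.97% vs 1% | 22% | 36% |

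**A few false answers in each arm at the planned rates.** With 149 per arm and rounded planned counts:

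| Events | Chi-square p | Fisher p |
|---|---|---|
| 12 vs 2 | 0.006 | 0.011 |
| 13 vs 3 | 0.010 | 0.018 |
| 14 vs 4 | 0.015 | 0.026 |

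The risk ratio falls from 12/2 = 6.0 to 14/4 = 3.5, but significance is kept.

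**The case against.** The outcome section says when the register must be used. It does not forbid checking a yes, and the Information sources section points towards eCAP. A reader might infer that every reached patient is scored on an unconfirmed word. The documents do not support that: the team offers help in making the document, so ADs completed that way are known directly, and the questions on the reason for formalising and on days to completion are partial checks. What stands is that neither is a confirmation rule, and that the Information sources section does not fit the outcome section.

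A reader might also infer that one or two stray answers in each arm would overturn the result. At the planned rates they would not, as the 14 vs 4 comparison shows.

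The chi-square false-positive figures should not be read alone. With about 1.5 control events and 4.4 to 5.9 intervention events (149 × 2.98% and 149 × 3.97%), the average of the two arms is below 5, so Fisher's test, which the plan also names, would ordinarily apply. It gives 9% and 22%, and at f = 1% about 2%, which is within the nominal 2.5%.

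The main objective as analysed combines interest with completion. Interest cannot be checked in a register and has no stated control rate, so these figures say nothing about that composite. Completion is nevertheless a listed outcome, the first hypothesis and the sole basis for the sample size.

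**Conclusion.** The point holds as an inconsistency in how AD completion is ascertained. It is framed and sized as a record, but the operational rule lets reached patients be scored on an unconfirmed answer and unreached patients on the register. This is worth correcting because the open-label design makes unequal reporting possible and the expected control count is under two.

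Its size depends wholly on the assumed f and applies to AD completion only. An equal error of 1% to 3% costs about 10 to 27 percentage points of power, depending on the test, and takes the risk ratio from 7.8 to between 4.4 and 2.7. An error of 2% to 3% confined to the intervention arm raises the chance of a false positive result to 9% to 22% (Fisher) or 21% to 36% (chi-square). The documents do not show that such errors will occur, only that nothing written would detect them. The sample size of 165 per arm is not in question: with a record-based outcome the planned rates still apply.

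**What to change.** Reconcile the protocol's hypothesis, Information sources, Result or dependent variables and analysis sections, and the SAP, with one definition. For example: AD completed means an AD seen in eCAP/HC3, or the formalised document seen at the health centre, dated within 3 months of recruitment.

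View eCAP/HC3 for all randomised patients in both arms, ideally by someone unaware of the arm. Looking up only those who are unreached or answer yes would leave reached patients who answer no scored on their word. Keep the patient's answer for interest, reasons and timing. Report self-reported but unregistered ADs by arm as a sensitivity analysis.

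The cost is a few sentences and about 2 × 165 = 330 look-ups through the access routes that the protocol already lists. The downside is small: a real AD made elsewhere, and neither registered nor brought to the centre, drops out of the main count in either arm. If the patient reports it, it appears in the sensitivity analysis.

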Bivariate analysis using as a dependent variable the answer yes or no to the realization of the VAD within the intervention group and as independent variables the basal characteristics. The Student's t test or the Mann-Whitney U test (according to the frequency distribution of the variables studied) will be used to compare continuous variables, and Chi-square or Fisher's exact test for comparison of categorical variables.

3 · "Evaluate the reasons why the document is formalized by open question": it will be categorized if there is a limited number of categories of responses and a descriptive univariate analysis will be done (frequency tables). In case of multiple answers the reasons will be described qualitatively.

4 · "Evaluate the average time to perform the DVA from the day of recruitment of the patient.": Univariate descriptive analysis.

SCHEDULE OF ACTIVITIES

- o Implementation of the protocol: From October 2014 to May 2015. Directed by [name], [name] and [name].
- o Ethical committee approval and health authorities: will be sent to USR Metropolitana Nord ([name]): April –June 2015. The shipment will be made by [name].
- o Recycling in advance wishes of the researcher: 2 sessions of 1 hour given by the lecturer: 2 days of May 2016.
- o Inclusion of the first and last patient: From 1 to 30 September 2016. Conducted by participating physicians: [name], [name], [name], [name], [name], [name], [name].
- o Completion of the last patient follow-up: From 1 to 30 December 2017. Conducted by participating physicians: [name], [name], [name], [name], [name], [name], [name].
- o Availability of results report: January-February 2017. Directed by [name]
- o Plan validation data: March 2017. Directed by [name]

NECESSARY RESOURCES

The study will be carried out at the Florida Nord EAP of L'Hospitalet de Llobregat, which has a long history as a teaching center attached to the Unitat Docent Multidisciplinary Family Medicine and Community of Ponent Coast.

Some of the researchers are tutors of this teaching unit.

The Florida Nord EAP has a computerized medical history since 2005.

We have the consultations, the computer resources and clinical tool consumable or inventoried necessary for the realization of the study. All visits and subpoenas will be in charge of the research team.

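### Interest obtained by asking at the 3-month contact is open to arm-aware questioning and courtesy answers, because the doctors who inform the patients are also listed as conducting follow-up

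*Protocol*

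**What the plan says.** **Who does what.** The main objective has primary care physicians give the information. Under Recruitment procedure, the allocation number is requested before the patient enters the room. The Schedule of activities lists the participating physicians for inclusion and again for follow-up: "Completion of the last patient follow-up: From 1 to 30 December 2017. Conducted by participating physicians". Necessary resources puts all visits under the research team. No independent assessor is named.

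**Masking.** The Sample section calls the trial open-label. The Design section says "Subsequent masking is not appropriate for the patient". Neither mentions the person who collects outcomes.

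**The outcome.** In the protocol and the SAP, the main objective is the proportion interested in, or completing, an advance directive in 3 months. Result or dependent variables makes interest a yes/no item. It counts patients who came to their doctor to ask and patients who showed interest by telephone. Where the patient has not already come forward, the information is sought by questioning at an appointment or by telephone. The electronic record is consulted for a directive only if the patient cannot be reached, and it shows completion, not interest.

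**The acknowledged limitation.** Limitations and ethical considerations names "Possible increase in response in the intervention group due to the link with the family physician (participation bias", accepts that it could lead to a wrong conclusion of effectiveness, and answers: "Randomization of the sample is intended to partially avoid this problem".

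**The concern.** In the intervention arm, the doctor has told the patient about directives, offered help and said that an answer is awaited within 3 months. If that doctor, or a colleague who knows the arm, later asks whether the patient is interested, two things can differ between arms without any true effect. The doctor may ask or code more generously, and the patient may give the answer that pleases. Control patients had no such offer to respond to.

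Randomisation makes the arms alike at baseline, including in how attached patients are to their doctor. It cannot act on what happens after allocation. Interest enters the main outcome directly, so any such difference goes into the effect estimate.

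**Working it through.** **1. The plan's own figure.** The only calculation is the sample size: "Accepting an alpha risk of 0.05 and a beta risk of 0.2 in a bilateral contrast", and "165 individuals in the intervention group and 165 in the control group are required", for completed directives at 7.8% versus 1%, with a 10% allowance. With the Poisson variance, the method the protocol names:

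- n = (1.960 + 0.842)² × (0.078 + 0.010) / (0.078 − 0.010)² = 7.849 × 0.088 / 0.004624 = 149.4 per arm.
- With the allowance: 149.4 / 0.9 = 166.0, or 149.4 × 1.1 = 164.3.

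The stated 165 is reproduced to within two patients. It contains no rate for interest, so the documents give no base rate for this point.

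**2. Is the exposure there?** Setting the sections side by side:

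| Step | Where | Content |
|---|---|---|
| Arm known | Recruitment procedure | Before the patient enters |
| Information given | Main objective; Intervention | By the physicians |
| Follow-up | Schedule of activities | By the participating physicians |
| Interest | Result or dependent variables | Partly by questioning |
| Script, threshold, masked assessor | Nowhere in protocol or SAP | – |

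**3. How much over-recording would matter?** Assumptions, none from the documents: 10% recorded interest in both arms if ascertained alike; no true effect; 165 analysed per arm; extra yes records in the intervention arm only.

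Test: z = (a − b) / √(2p(1 − p)/165), where a and b are the observed proportions and p is their mean. Reject if |z| > 1.96. The rejection probability is the sum of the binomial probabilities over all pairs of counts that reject.

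| Extra points, intervention arm | Recorded rates | Chance of a significant result |
|---|---|---|
| 0 | 10% v 10% | 5.1% |
| 1 | 11% v 10% | about 6% |
| 2 | 12% v 10% | about 9% |
| 3 | 13% v 10% | about 14% |
| 5 | 15% v 10% | about 28% |
| 10 | 20% v 10% | about 73% |

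**4. Sensitivity of the 5-point row.**

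- If questioning also lifts controls by 2.5 points (15% v 12.5%), 28% falls to about 10%.
- With base rates of 5%, 20% and 39%, the result is about 41%, 19% and 15%. The 39% is the share in a primary care survey cited in the introduction who said they would complete a directive.

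**5. The same in patients.** With 16 of 165 controls recorded as interested, the uncorrected chi-square test needs 29 of 165 in the intervention arm (p = 0.037; 28 gives 0.052). That is 13 extra, or 13/165 = 7.9 points, and 13/7 = about 1.9 per doctor.

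**The case against.** A reader might infer that each doctor questions and judges his or her own patients. The documents do not say so. Result or dependent variables does not state who asks or who classifies. The link is the schedule line, which assigns follow-up to the doctors as a group. This objection stands, but an unspecified questioner is not a safeguard.

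A reader might also infer that interest is wholly subjective and leaves no record. That is too strong. Coming to ask, booking an appointment, or leaving details at the User Service is behaviour that can be dated. The exposed part is interest brought out by questioning.

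Nor is the direction settled. Both arms are questioned, and raising the subject with controls may itself create interest and shrink the difference.

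The protocol does not claim that randomisation solves the doctor-link problem, only that it partly avoids it. Its abstract objective, first hypothesis and sample size concern completed directives, which are less exposed. Both points limit the weight of the concern. They do not remove it, because the stated main objective, repeated in the SAP, includes interest.

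Finally, the open-label design is not the fault. Patients cannot be masked to being given information. What can be separated is giving the information and asking about its result.

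**Conclusion.** The point holds for elicited interest, and it should be corrected. The plan lets people who know the arm, and who delivered the intervention, obtain part of the main outcome by unscripted questioning. Its stated remedy, randomisation, does not reach a bias that arises after allocation. The bias more probably favours the intervention, but that is a judgement and not something the documents establish.

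Its size is unknown. One to three points of one-sided over-recording would raise the false-positive risk modestly, to about 6% to 14%. Five points would raise it to 28% and ten to 73%. All of these rest on the assumed 10% base rate, no true effect and no matching rise in controls. They show sensitivity and do not predict what would happen in this trial.

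**What to change.** For the 3-month contact:

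1. The seven doctors exchange lists, so that each contacts another doctor's patients. The list gives name, telephone number and due date, but not the arm.
2. One fixed question set on interest and completion is put to both arms in the same words, before any talk of the first visit.
3. The open question on reasons and the contamination questions to controls come only after interest and completion are recorded, because they can reveal the arm.
4. The patient's own doctor and the User Service only record and date requests that the patient brings.
5. Directives are checked on the register for every patient, not only for those who cannot be reached.
6. The SAP reports patient-initiated requests and registered directives separately from elicited interest.

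**Cost.** No extra staff or visits and no change in sample size. It needs a list without the arm, a short script and a register look-up for all 330 patients. The consent must cover sharing contact details among the study doctors, since the protocol has consent requested through the patient's physician.

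**Downsides.** Some patients may answer an unfamiliar doctor less readily, and some will reveal their arm. The caller is still a study doctor, so the bias is reduced and not removed.
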